5.3. Study cohort/ data sets to be analysed

5.3.1. Total cohort

The Total cohort will comprise of all eligible subjects included in the study.

5.4. Derived and transformed data

- Influenza is defined as any positive laboratory test from one or more of the clinical specimens [[Guidelines for the epidemiological surveillance of influenza](#), 2012].

5.5. Statistical methods

5.5.1. Analysis of demographics/baseline characteristics

Demographic characteristics (age and gender) will be summarised by group using descriptive statistics:

- Frequency tables will be generated for categorical variable such as gender.
- Mean, median and standard deviation will be provided for continuous data such as age.
- The distribution of influenza cases by month and year will also be tabulated.

5.5.2. Analysis of primary objective

The proportion of subjects with influenza caused by seasonal influenza A and/or B among all influenza cases reported with exact 95% confidence interval (CI) by age, A-virus subtype and B-strain lineage and overall will be calculated.

5.5.3. Analysis of secondary objectives

Seasonal influenza A and/or B cases will be described using frequency and percentages by temporal (calendar weeks/months) and geographical distributions (by country and by region within the country [if data is available]) within different influenza seasons (2010-2011, 2011-2012, 2012-2013, 2013-2014 and 2014-2015). Frequency and percentage for clinical features and outcomes (clinical manifestations, duration of illness, complications) experienced by influenza positive subjects will be tabulated by type of influenza (seasonal influenza A and/or B) in different seasons from 2010-2015. Frequency and percentage for influenza B lineages by age (<1, 1-4, 5-9, 10-14, 15-19, 20-24, 25-44, 45-49, 50-59, 60-64 and ≥ 65 years) and region will also be provided.

The characteristics of the influenza B-infection as observed in the database and the B strain included in the trivalent influenza vaccine will be assessed using frequency and percentage for each year. The proportion of matched B-strains and mis-matched B-strains will be estimated along with 95% CI.

5.6. Interpretation of analyses

All the analyses with respect to the primary and secondary endpoints will be descriptive. These descriptive analyses will not be interpreted, except describing the study results.

5.7. Conduct of analyses

Any deviation(s) or change(s) from the original statistical plan outlined in this protocol will be described and justified in the final study report.

5.7.1. Sequence of analyses

The final analysis will be performed when all required data for the study have been extracted from the ICGES database and transferred to the sponsor or to the site of analysis, as applicable.

5.7.2. Statistical considerations for interim analyses

All analyses will be conducted using the final data and no statistical adjustment will be required as no interim analysis is planned for this study.

6. CONDUCT OF THE STUDY

6.1. Regulatory and ethical considerations

The study will be conducted in accordance with all applicable regulatory requirements, including all applicable subject privacy requirements and the guiding principles of the Declaration of Helsinki.

GlaxoSmithKline Biologicals (GSK Biologicals) will seek favourable opinion/approval to conduct the study prior to data extraction or will document that neither a favourable opinion nor an approval to conduct the study is needed.

Conduct of the study includes, but is not limited to, the following:

- Institutional Review Board (IRB)/Independent Ethics Committee (IEC) review and favourable opinion/approval of study protocol and any subsequent amendments.
- Investigator reporting requirements as stated in the protocol.

GSK will provide full details of the above procedures to the investigator, either verbally, in writing, or both

6.2. Informed consent

Prior to the data processing and analysis, all data will be anonymised. GSK Biologicals personnel and delegates will not be able to make a link between the data and specific individuals. Therefore no patient consent is needed. For further details see Section [6.3](#).

6.3. Data privacy

Data privacy is protected by using anonymised data (see [glossary of terms](#)).

The ICGES database is fully coded. No GSK Biologicals personnel will have the ability to link data to an identifiable individual.

6.4. Outline of data extraction procedures

Table 3 presents the list of data extraction procedures.

Table 3 List of data extraction procedures

Epoch: Retrospective data collection
Identification of eligible study cases in ICGES influenza national surveillance program database
Identification and anonymisation of eligible subjects
Extraction of individual data
Dataset check and transfer from ICGES to GSK
Handling of incomplete data, missing data and discrepancies

6.5. Detailed description of data extraction and handling procedures

6.5.1. Identification of eligible study cases in ICGES influenza national surveillance program database

The ICGES database of Panama will be checked for all seasonal influenza A and/or B positive cases reported via influenza surveillance programs from 2010 to 2015.

6.5.2. Identification and anonymisation of eligible subjects

All subjects with a laboratory diagnosis of seasonal influenza A and/or B, will be identified from this database. The data present in ICGES database is already anonymised, therefore subject identification number allocation is not required.

6.5.3. Extraction of individual data

All seasonal influenza A and/or B cases reported in the ICGES database will be validated and extracted in the required file format e.g. Statistical Analysis System (SAS) datasets. The following data will be collected for seasonal influenza A and/or B positive subjects:

- Demographic data such as age and gender.
- Data on A-virus subtype and B-strain lineage (when available), geographic region, clinical features and outcomes (clinical manifestations, duration of illness, complications) etc.

6.5.4. Database check and transfer from ICGES to GSK

ICGES will transfer the data files extracted for the study on GSK SAS Drug Development (SDD) secured web platform (SDD) as SAS data sets (if data cannot be provided by ICGES in SAS format, GSK can alternatively accept Excel spreadsheets).

Additionally to the data sets, ICGES will provide a description of each data set, including a description of each column and its attributes (data type, length and as applicable, decodes if codes are used, and coding dictionary reference for codes and terms related to a specific coding and terminology system like ICD-10, SNOMED, WHOART, MedDRA, ...).

6.5.4.1. Check of data set content and format

Prior to starting the programming of the analyses, the GSK person responsible for the analyses will check if the data files content and format meet the requirements for the statistical analyses. This will include (but will not be limited to) checks on the subject/case identifiers consistency, checks on the presence of the analyses variables, checks on list of values and/or codes and checks on the numeric and date formats. Any finding will be feedback to ICGES database owner and require a new transfer, until content and format are appropriate for the statistical analyses.

6.5.4.2. Check of data completeness and consistency

Any data deficiency such as incomplete data, missing data and data discrepancies that would be detected by GSK statistician or epidemiologist and that are critical for the analyses will be feedback to ICGES database owner. Depending on the possibility of the database owner to correct data, corrected data will be retransferred or not to GSK.

6.5.5. Handling of incomplete data, missing data and discrepancies

As applicable, the rules taken for handling incomplete data, missing data and data discrepancies in statistical analyses will be documented in the SAP (e.g.: handling missing data and codes such as 'UNK', 'N/A', 'ND'; calculation of a duration from partial dates; censoring of discrepant data ...)

7. ADMINISTRATIVE MATTERS

To comply with regulatory requirements and GSK standards, administrative obligations relating to protocol amendments, protocol administrative changes and termination of the study must be fulfilled.

7.1. Record retention

The datasets sent by the database owner will be loaded and archived at GSK as per the applicable requirements and the retention policies.

The minimum retention time will meet the strictest standard applicable for the study, as dictated by the applicable guidelines or applicable laws or regulations, or GSK standards/procedures; otherwise, the minimum retention period will default to 30 years.

7.2. Quality assurance

To ensure compliance with Good Clinical Practice (GCP) or other applicable guidelines and all applicable regulatory requirements, GSK may conduct a quality assurance audit. Regulatory agencies may also conduct a regulatory inspection of this study. Such audits/inspections could occur at any time during or after completion of the study. If an audit or inspection occurs, the database owner and institution agree to allow the auditor/inspector direct access to all relevant documents and to allocate his/her time and the time of his/her staff to the auditor/inspector to discuss findings and any relevant issues.

7.3. Posting of information on publicly available clinical trial registers and publication policy

Database studies that do not evaluate vaccines/products are progressed for publication in the scientific literature when the results provide important scientific or medical knowledge.

7.4. Provision of study results to investigators

Where required by applicable regulatory requirements, an investigator signatory will be identified for the approval of the study report. The investigator will be provided reasonable access to statistical tables, figures, and relevant reports and will have the opportunity to review the complete study results at a GSK site or other mutually-agreeable location.

8. COUNTRY SPECIFIC REQUIREMENTS

IRB approval for epidemiological observational studies.

APPENDIX A CURRENT DATABASE STATISTICS FOR PANAMA

[figure not shown]
Circulation of Influenza Viruses 2010-2014³

[figure not shown]
[figure not shown]
Number of specimens positive for influenza by subtype

Circulation of Influenza Viruses 2010-2014³

Number of specimens positive for influenza by subtype

Circulation of Influenza Viruses 2010-2014³

Number of specimens positive for influenza by subtype

**LIST OF ABBREVIATIONS**

CI	Confidence Interval
CTRS	Clinical Trial Registry Summary
DB	Database
GSK	GlaxoSmithKline
ICGES	Instituto Conmemorativo Gorgas de Estudios de la Salud
LL	Lower Limit of the confidence interval
N.A.	Not Applicable
SAP	Statistical Analysis Plan
SD	Standard Deviation
SLIPE	Sociedad Latinoamericana de Infectología Pediátrica
SR	Study Report
TFL	Tables Figures and Listings
TIV	Trivalent Influenza Vaccines
TOC	Table of Content
UL	Upper Limit of the confidence interval

## 1. DOCUMENT HISTORY

Date	Description	Protocol Version
20-SEP-2017	Final version	Final Version 1: 29 March 2016

## 2. STUDY DESIGN

- Type of study: Self-contained.
- Type of design: Epidemiological, non-interventional, observational, retrospective, database study.
- Study population: All subjects who have laboratory confirmed diagnosis of influenza (laboratory confirmed case) and reported in the national influenza surveillance system in selected countries from the Year 2010-2015.
- General study aspects: All seasonal influenza A and/or B cases reported in the ICGES database will be screened. Demographic data, date of onset of the first symptom and data on A-virus subtype and B-strain lineage, geographic region where the virus was isolated, clinical features and outcomes (clinical symptoms, duration of illness, complications) experienced by all influenza positive subjects (subjects with a laboratory confirmed influenza diagnosis) will be validated, extracted and transferred from the ICGES database to the sponsor or to the site of analysis, as applicable.
- Period of data collection: The study will include data on all the subjects with a laboratory confirmed influenza diagnosis, reported in the ICGES database of Panama, from January 2010 to December 2015. For all eligible subjects, individual level anonymised and key coded data will be collected from the database.
  - Epoch 001: Retrospective data collection.

**Table 1      Study group and epoch foreseen in the study**

Study Group	Epoch
	Epoch 001
Retrospective	x

### 3. OBJECTIVES

#### 3.1. Primary objective

- To describe seasonal influenza A and/or B cases by age and virus subtype (AH1N1/A H3N2) and B-strain lineage (Victoria and Yamagata) using data reported via National Surveillance Program in Panama, selected countries of Central America and the Caribbean from January 2010 to December 2015.

#### 3.2. Secondary objectives

From January 2010 to December 2015, in each selected country:

- To describe clinical features and outcomes (clinical manifestations, duration of illness, complications) of seasonal Influenza A and B cases in (overall and by subtypes or lineages) different seasons.
- To describe the temporal and geographical distribution of seasonal influenza A and/or B (overall and by subtypes or lineages) cases within different seasons.
- To estimate the percentage of co-circulation of influenza B lineages (Yamagata and Victoria lineages) among the study population, by age categories and by region.
- To describe the mismatch between the B-strain included in the Trivalent Influenza Vaccines (TIV) and the circulating B strains in different seasons.

### 4. ENDPOINTS

#### 4.1. Primary endpoint

- Occurrence of seasonal influenza A and/or B cases by age, virus subtype and strain lineage from the January 2010 to December 2015, in Panama, selected countries of Central America and the Caribbean (using the data reported via National Influenza Surveillance Program).

#### 4.2. Secondary endpoints

- Occurrence of clinical features and outcomes (clinical symptoms, duration of illness, complications) experienced by subjects who have laboratory confirmed diagnosis seasonal influenza A and/or B, in different seasons from 2010 to 2015.
- Frequency of seasonal influenza A and/or B cases reported in different temporal and geographical locations within different seasons from 2010 to 2015.
- Occurrence of influenza caused by B-strain and presented by B lineages among the study population, by age (<1, 1-4, 5-9, 10-14, 15-19, 20-24, 25-44, 45-49, 50-59, 60-64 and ≥ 65 years) and by region.
- Compare the characteristics of the influenza B-infection as observed in the database and the B-strain included in the trivalent influenza vaccine.

## **5. ANALYSIS SETS**

### **5.1. Definition**

#### **5.1.1. Screened cohort**

The screened cohort will include all the specimen samples received per year within the ICGES influenza surveillance system for influenza testing at aggregated level

#### **5.1.2. Total cohort**

The Total cohort will comprise of all eligible subjects included in the study.

### **5.2. Criteria for eliminating data from Analysis Sets**

Not applicable for database studies

## **6. STATISTICAL ANALYSES**

Note that standard data derivation rule and stat methods are described in annex 1 and will not be repeated below.

All the analysis on primary and secondary objectives will be performed on Total cohort.

### **6.1. Demography**

#### **6.1.1. Analysis of demographics/baseline characteristics planned in the protocol**

Demographic characteristics (age and gender) will be summarised by group using descriptive statistics:

- Frequency tables will be generated for categorical variable such as gender.
- Mean, median and standard deviation will be provided for continuous data such as age.
- The distribution of influenza cases by month and year will also be tabulated.

#### **6.1.2. Additional considerations**

Number of specimen samples received per year within the ICGES influenza surveillance system for influenza testing will be tabulated using frequency and percentages by calendar year and by Southern Hemisphere/Northern Hemisphere influenza season

## 6.2. Primary objective

### 6.2.1. Analysis of primary objective planned in the protocol

The proportion of subjects with influenza caused by seasonal influenza A and/or B among all influenza cases reported with exact 95% confidence interval (CI) by age, A-virus subtype and B-strain lineage and overall will be calculated.

### 6.2.2. Additional considerations

None

## 6.3. Secondary objectives

### 6.3.1. Analysis of secondary objectives planned in the protocol

Seasonal influenza A and/or B cases will be described using frequency and percentages by temporal (calendar weeks/months) and geographical distributions (by country and by region within the country [if data is available]) within different influenza seasons (2010-2011, 2011-2012, 2012-2013, 2013-2014 and 2014-2015). Frequency and percentage for clinical features and outcomes (clinical manifestations, duration of illness, complications) experienced by influenza positive subjects will be tabulated by type of influenza (seasonal influenza A and/or B) in different seasons from 2010-2015. Frequency and percentage for influenza B lineages by age (<1, 1-4, 5-9, 10-14, 15-19, 20-24, 25-44, 45-49, 50-59, 60-64 and ≥ 65 years) and region will also be provided.

The characteristics of the influenza B-infection as observed in the database and the B strain included in the trivalent influenza vaccine will be assessed using frequency and percentage for each year. The proportion of matched B-strains and mis-matched B-strains will be estimated along with 95% CI.

### 6.3.2. Additional considerations

Influenza A and/or B specimens (overall and by subtypes or lineages) will be described using frequency and percentages by country as well as Southern Hemisphere or Northern Hemisphere influenza season (depending which hemisphere influenza season the country follows). Example: Panama, El Salvador, Trinidad are considered as southern hemisphere and Guatemala, Dominican republic as northern hemisphere.

The proportion of mismatched B lineage will be calculated as 1 minus proportion of matched B lineage and expressed as percentages.

## 7. ANALYSIS INTERPRETATION

All the analyses with respect to the primary and secondary endpoints will be descriptive. These descriptive analyses will not be interpreted, except describing the study results.

## 8. CONDUCT OF ANALYSES

### 8.1. Sequence of analyses

There will be an interim analysis perform on available data (lab database for Panama) to submit the abstract/poster to SLIPE congress with preliminary results. The final analysis will be performed when all required data for the study have been extracted from the ICGES database and transferred to the sponsor or to the site of analysis, as applicable.

Description	Analysis ID	Disclosure Purpose (CTRS=public posting, SR=study report, internal)	Dry run review needed (Y/N)	Study Headline Summary (SHS)requiring expedited communication to upper management (Yes/No)	Reference for TFL
Analysis for abstract/poster submission to SLIPE congress	E1_01	Abstract/poster submission	N	No	TFL TOC-Abstract/poster submission (column J)
Final Analysis of epoch 1	E1_02	SR, CTRS	N	Yes	TFL TOC - All TFLs

### 8.2. Statistical considerations for interim analyses

All the analyses with respect to the primary and secondary endpoints will be descriptive/exploratory. As the results of the interim analyses will not be used to alter the study conduct, no statistical adjustment for interim analyses is required.

## 9. CHANGES FROM PLANNED ANALYSES

- There will be an interim analysis planned on available data (lab database for Panama) in order to submit the abstract\poster for SLIPE congress
- We will also be reporting the number of specimen samples received per year within the ICGES influenza surveillance system for influenza testing at aggregated level (considered as screened cohort) and determine the proportion that tested positive for Influenza to describe the reporting capabilities of the surveillance system at capturing influenza A and B cases.
- We will also be including seasonal 2016 data as it is presently available. Based on the dates of data transfer, the end time period may be expanded if data is available during data transfer
- All the statistical analysis will be performed on specimens instead of subjects because a subject can provide more than one influenza positive specimens.
- The age group used for the analysis are 0-4, 5-17, 18-49, 50-64 and >=65 years instead of <1, 1-4, 5-9, 10-14, 15-19, 20-24, 25-44, 45-49, 50-59, 60-64 and ≥ 65 years.

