4.2. Inclusion criterion

Deviations from inclusion criteria are not allowed because they can potentially jeopardize the scientific integrity of the study or regulatory acceptability. Therefore, adherence to the criteria as specified in the protocol is essential.

All subjects must satisfy the following criterion at study entry:

- All subjects diagnosed with seasonal influenza A and/or B, reported in the ICGES database of Panama, from January 2010 to December 2015.

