5. STATISTICAL METHODS

5.1. Endpoints

5.1.1. Primary endpoint

- Occurrence of seasonal influenza A and/or B cases by age, virus subtype and strain lineage from the January 2010 to December 2015, in Panama, selected countries of Central America and the Caribbean (using the data reported via National Influenza Surveillance Program).

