## 10. LIST OF FINAL REPORT TABLES, LISTINGS AND FIGURES

The TFL TOC provides the list of tables/listings and figures needed for the study report. It also identifies the tables eligible for each analyses and their role (synopsis, in-text, post-text, SHS, CTRS). Note that all TFL aimed to be included as post-text are noted as post-text even if these are tabulation of individual data such as listing of SAE. The post-text material contains all source material for the study report and accordingly a post-text table may be redundant with an in-text table.

The mock tables referred under column named 'layout' can be found in **PPD** **PPD** dedicated folder for standard tables and in Annex 3 for study specific mock table/figure/listing. The latter table/figure/listing are identified by the prefix SS\_ in the TFL Toc.

The following group names will be used in the TFLs:

Group order in tables	Group label in tables	Group definition for footnote
P	Influenza A	Positive for Influenza A
P	Influenza B	Positive for Influenza B
Or/and		
P	H1N1	Positive for Influenza A subtype H1N1
P	H3N2	Positive for Influenza A subtype H3N2
Or/and		
P	Victoria	Positive for Influenza B lineage Victoria
P	Yamagata	Positive for Influenza B lineage Yamagata
Or/and		
P	0-4	0-4 years of age
P	5-17	5-17 years of age
P	18-49	18-49 years of age
P	50-64	50-64 years of age
P	>=65	>=65 years of age
Or/and		
P	West	West: Boca del Toro, Chiriquí and Comarca Nobe Bugle
P	Central	Central: Coclé, Herrera, Los Santos and Veraguas
P	Panama	Panamá: Panamá Este, Panamá Oeste, Panamá Metro and San Miguelito
P	Northeast	Northeast: Colón, Darién and Kuna Yala

Influenza season		
Calendar year (Jan-Dec)	Southern Hemisphere (May-Oct)	Northern Hemisphere (Oct-May)
Jan-Dec 2010	May– Oct 2010	Oct 2010-May 2011
Jan-Dec 2011	May– Oct 2011	Oct 2011-May 2012
Jan-Dec 2012	May– Oct 2012	Oct 2012-May 2013
Jan-Dec 2013	May– Oct 2013	Oct 2013-May 2014
Jan-Dec 2014	May– Oct 2014	Oct 2014-May 2015
Jan-Dec 2015	May– Oct 2015	Oct 2015-May 2016
Jan-Dec 2016	May– Oct 2016	Oct 2016-May 2017

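### The SAP adds 2016 and leaves the end date open, so the January 2010 to December 2015 result by age and region that the primary endpoint defines is never tabulated

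*SAP*

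**What the plan says.** - Protocol section 4.2 admits cases "reported in the ICGES database of Panama, from January 2010 to December 2015". The same section adds: "Deviations from inclusion criteria are not allowed because they can potentially jeopardize the scientific integrity of the study".
- The primary endpoint has the same window in Protocol section 5.1.1 ("strain lineage from the January 2010 to December 2015, in Panama") and in SAP section 4.1 ("virus subtype and strain lineage from the January 2010 to December 2015"). SAP sections 2 and 3.1 also keep it.
- SAP section 5.1.2 limits the Total cohort to eligible subjects, and the protocol glossary ties eligibility to the inclusion and exclusion criteria. SAP section 6 runs all primary and secondary analyses on that cohort.
- SAP section 9 brings in 2016 because those data are already available, and then says that "the end time period may be expanded if data is available during data transfer". No closing date appears anywhere. The SAP is dated 20 September 2017, so part of 2017 could also enter.
- The mock tables follow section 9. Templates 17-22 have 2016 rows above a Total line, and Templates 5-10 run to December 2016. Templates 3-4, 11-16 and 32-33 have no year or season rows.
- The season table in SAP section 10 runs to "Oct 2016-May 2017", while the protocol text repeated in SAP section 6.3.1 stops at 2014-2015.

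**The concern.** The endpoint is a proportion over a stated period, and in a descriptive study that period is a large part of what the estimate means. If the end date depends on when data arrive, the pooled figures describe a period that nobody has fixed in advance.

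This matters because influenza B is very uneven from year to year. In Table 2 of the protocol it is absent in 2011 and 2013 and is the majority of positives in 2012. One more year can therefore move a pooled share visibly. The primary objective is a description by age, and the tables that deliver it with exact intervals (Templates 11-13) are among those with no year split. A reader who wants the 2010-2015 result by age could not rebuild it from the planned output.

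**Working it through.** **1. Inputs (Protocol section 5.2, Table 2, Panama only).** Influenza positives and B positives: 2010, 207 and 14; 2011, 47 and 0; 2012, 276 and 178; 2013, 190 and 0; 2014, 140 and 55. The protocol's stated range of 47 to 276 positives per year is the minimum (2011) and maximum (2012) of this column, so it is reproduced.

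**2. B share by year.** 14/207 = 6.8%; 0/47 = 0%; 178/276 = 64.5%; 0/190 = 0%; 55/140 = 39.3%. Pooled 2010-2014: 247/860 = 28.7% (Clopper-Pearson 95% CI 25.7% to 31.9%).

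**3. Six-year base.** The endpoint covers six years and the documents give no 2015 count. Assumption: 2015 equals the Table 2 average, that is 860/5 = 172 positives and 247/5 = 49.4 B. The 2010-2015 base is then (247 + 49.4)/(860 + 172) = 296.4/1032 = 28.7%. With 49 whole cases, 296/1032 has a 95% CI of 25.9% to 31.5%.

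**4. Add a 2016 that repeats one Table 2 year.** Pooled share = (296.4 + B)/(1032 + positives). Shifts are taken before rounding.

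| 2016 like | B / positives, 2010-2016 | Pooled B share | Shift (points) |
|---|---|---|---|
| 2010 | 310.4 / 1239 | 25.1% | -3.7 |
| 2011 | 296.4 / 1079 | 27.5% | -1.3 |
| 2012 | 474.4 / 1308 | 36.3% | +7.5 |
| 2013 | 296.4 / 1222 | 24.3% | -4.5 |
| 2014 | 351.4 / 1172 | 30.0% | +1.3 |

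The weight of 2016 in the pool ranges from 47/(1032 + 47) = 4.4% to 276/(1032 + 276) = 21.1%.

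**5. Which tables can be separated.**

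- Templates 17, 19 and 21 print n and N for each calendar year. Adding the rows for 2010 to 2015 gives the overall proportions by type, subtype and lineage, and an exact interval can be computed from the sums.
- Templates 11-13 (by age) and 14-16 (by region) give one column per group over the whole period. Templates 3-4 (demography) and 32-33 (background information) are also unsplit. Nothing in the planned output lets 2016 be taken out of them.

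The shares in step 4 are what the Total column of Template 11 would show under each scenario. The documents give no counts by age or region, so the shift within a group cannot be computed.

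**6. Seasons.** A northern season (October to May) has 8 months. A December 2015 cut-off leaves 3 of them (October to December) in the 2015-2016 season. If data ended in December 2016, the 2016-2017 season would likewise hold 3 of 8.

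**The case against.** The strongest reply is that the extension is open and legitimate. SAP section 9 is the place for changes, and the SAP elsewhere repeats protocol wording that section 9 then replaces; section 4.2, for example, still lists the old age bands. Protocol section 5.7 accepts changes to the statistical plan if the report describes and justifies them. The rule against deviations is phrased for subjects at study entry and is weak evidence against a documented, study-wide extension. The analyses are descriptive, so there is no type I error to protect, and the trigger for a later end date is data availability, not results. All of this stands. It does not supply a cut-off date or a 2010-2015 table by age. The SAP also cites only the final version 1 protocol of 29 March 2016, with no amendment to the criterion.

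Four stronger readings are tempting and are not supported:

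- *No 2010-2015 result exists at all.* The yearly rows of Templates 17, 19 and 21 give it overall.
- *The last northern season will be shown incomplete.* It could be. But the SAP postdates May 2017, its open-ended sentence could admit a full season, and SAP Annex 3 calls the mocks illustrative. Panama is treated as following the southern season.
- *Country comparisons are spoiled.* Each template is for one country and no comparison between countries is planned. Different end dates by country are possible but are not stated.
- *The B share could move to 37.4% or 23.5%.* Those figures, 425/1136 and 247/1050, add a year to 2010-2014. The endpoint covers six years.

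**Conclusion.** The point holds in a limited form. The SAP contradicts its own endpoint period and names no closing date. As a result, the tables without a year split will not give the result for the defined period by age or by region. The overall figures are recoverable, and single-year rows are unaffected.

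Under the stated assumption for 2015, the pooled B share could move from 28.7% to between 24.3% and 36.3%. Three of the five scenarios (2010-, 2011- and 2014-like) stay within 4 points. The movement could be near zero if 2016 resembles the pooled average. The illustration rests on Panama data alone and on assumed 2015 and 2016 counts. The consequence is for what the estimates and intervals describe, not for any test.

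**What to change.** 1. In SAP section 9, state one calendar data cut-off for all countries and delete the open-ended sentence. Make SAP sections 2, 3.1, 4.1 and 5.1.2 and the season lists agree with it.
2. Produce Templates 3-4, 11-16 and 32-33, and all Total rows, for January 2010 to December 2015 as the primary version. Show 2016 separately or in a supplementary 2010-2016 total.
3. Flag any season that the applicable cut-off truncates: October 2015 to May 2016 under the December 2015 window, and October 2016 to May 2017 if data end in December 2016. The first flag is needed because holding to December 2015 itself splits a northern season, which SAP section 6.3.2 applies to Guatemala and the Dominican Republic.

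The cost is some SAP wording and one extra version of some tables. The headline total will leave out data already in hand, but the supplementary total keeps them in the report.
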